#### **4.4 Exclusion Criteria: Cohorts 2 and 3**

Moderate to severe AD patients presenting with any of the following will not be included in the study:

- 1 AD of such severity (EASI >48) that the subject could not comply with the demands of the study and/or the subject is not a suitable candidate for a placebo-controlled study.
- 2 Have concomitant skin disease or infection (e.g. acne, impetigo) or presence of skin comorbidities in the study area to be dosed that may interfere with study assessments.
- 3 Patients who are hirsute in areas of skin to be dosed with study ointment.
- 4 Patients who are unwilling to stop hair removal by any means (including shaving, waxing or depilatory creams) to skin areas to be dosed with study ointment for 2 weeks prior to randomisation and throughout the duration of the study.
- 5 Hypersensitivity to any excipients in the study ointment formulation, study emollient or study shower cream
- 6 Hypersensitivity to any laundry detergents (Cohort 2 only).
- 7 Have received phototherapy (e.g. UVA, UVB or PUVA therapy), or systemic therapy (e.g. immunosuppressants [such as cyclosporine, azathioprine, methotrexate], cytostatics) known or suspected to have an effect on AD, within 4 weeks of the start of the study. All other biologics should not have been used within 3 months of the start of study.
- 8 Have received systemic corticosteroids (e.g. oral, intravenous, intraarticular, rectal) within 4 weeks of the start of the study. Subjects on a stable maintenance dose (over the preceding 3 months) of inhaled or intranasal CS may participate.
- 9 Patients treated with oral antihistamines or topical calcineurin inhibitors or topical steroids within 7 days of starting study; intranasal antihistamines for the treatment of allergic rhinitis are acceptable.
- 10 Use of a tanning booth/parlour/sunbathing (including excessive exposure to sunlight) or use of tanning products within 4 weeks before start of the study and for the duration of their participation in the study.
- 11 Have used antiseptic treatments (e.g. bleach baths, potassium permanganate etc.) within 4 weeks before the start of the study. (Patients who have recently used antiseptic treatment

may be rescreened at a later date if they wish to participate in the study and agree to stop antiseptic treatment.)

- 12 History of sensitivity to nonsteroidal anti-inflammatory drug(s) (NSAIDs).
- 13 Patients who have evidence of significant concomitant clinical disease that could interfere with the conduct or safety of this study, based upon a complete medical history, full physical examination, and a 12-lead resting ECG and laboratory safety tests. For example the presence of any other acute and/or unstable clinical disease, other than AD, such as:
- Poorly controlled Type I or Type II diabetes.
  - Seizure disorder or epilepsy.
  - Cerebrovascular accident.
  - Active or latent infection (eg, hepatitis).
  - Cancer (other than cutaneous basal cell) in the last 5 years.
  - Congestive heart failure.
  - Coronary artery disease.
  - Renal insufficiency and/or serum creatinine  $>1.5$  X upper limit of normal (ULN). Subjects with serum Creatinine  $<2$  X ULN may be retested once.
  - A major surgical operation during the 30 days prior to screening.

Stable well-controlled chronic conditions such as controlled hypertension [excluding those on  $\beta$ -blockers, calcium channel blockers (Class I or II)], thyroid disease, well-controlled Type 1 or Type 2 diabetes, hypercholesterolemia, gastroesophageal reflux, or depression under control with medication (other than tricyclic antidepressants), are acceptable provided the symptoms and medications would not be predicted to compromise safety or interfere with the tests and interpretations of this study.

- 14 Clinically significant cardiac disease or ECG abnormalities, including:
- Predominant heart rhythm other than normal sinus rhythm
  - AV block greater than first degree
  - Resting pulse rate  $>100$  or  $<50$  bpm
  - Electrocardiographic evidence or a history of myocardial infarction
  - Electrocardiographic evidence of conduction system abnormality
  - Subjects with pre-randomisation evidence of QTc prolongation (defined as  $>450$  msec).

The PI should decide whether ECG abnormalities other than those listed are clinically significant and should exclude the subject from enrolment.

- 15 Patients with a personal or family history of prolonged QTc interval.
- 16 Clinically significant liver function tests (LFTs; AST, ALT, total Bilirubin) Subjects with LFTs  $>1.5$  X ULN and  $<2$  X ULN may be retested once.
- 17 Positive HIV, HBsAg and HBcAb result or positive anti-hepatitis C virus serology (as determined by multi-antigen EIA)
- 18 Pregnant and nursing females.

- 19 Donation or intent to donate blood, or blood components during the study or within one month after completion of the study.
- 20 Patients who have received treatment with an investigational drug within 3 months prior to screening.
- 21 Patients with a known history (of at least 2 years) of drug abuse.
- 22 A positive urine drug screen.
- 23 Patients who are smokers (including patients who use nicotine substitutes). (Cohort 2 only)
- 24 History of regular alcohol consumption exceeding 21 drinks/week in males and 14 drinks/week in females (1 drink = 150 mL of wine or 360 mL of beer or 45 mL of spirits) within 6 months of screening.
- 25 Patients using potent CYP3A4 inhibitors (i.e, cimetidine, clarithromycin, cyclosporine, danazol, dexamethasone, diethyldithiocarbamate, erythromycin, fluconazole, fluoxetine, grapefruit juice, ketoconazole, metronidazole, norfloxacin, omeprazole, ranitidine, sertraline, valproic acid)
- 26 Inability to comprehend or unwilling to follow the study requirements including restrictions on treatments use of study emollient, attendance at out-subject clinic visits and participation in laboratory testing as called for by the protocol.
- 27 Any other severe acute or chronic medical or psychiatric condition or laboratory abnormality that may increase the risk associated with study participation or investigational product administration or may interfere with the interpretation of study results and, in the judgment of the investigator in discussion with the Ziarco CMO, would make the subject inappropriate for entry into this study.

#### **4.5 Life Style Guidelines: Cohorts 1 and 2**

The following life-style guidelines affect all subjects in Cohorts 1 and 2:

##### **Meals and Dietary Restrictions**

Water may be consumed without restriction. Non-caffeinated drinks (except grapefruit or grapefruit-related citrus fruit juices - see below) may be consumed with meals and the evening snack.

Subjects will be fasted from midnight.

Breakfast will be provided approximately 1 hour before the morning application except on Days 1 and Day 7 when no food will be provided until after the 4 hours post dose assessments have been completed.

Lunch will be provided approximately 4 hours after the morning application.

Dinner will be provided approximately 9 to 10 hours after the morning application.

An evening snack will be permitted.

Subjects will not be allowed to eat or drink grapefruit or grapefruit-related citrus fruits (eg, Seville oranges, pomelos) from 7 days prior to the first dose of study medication until collection of the final pharmacokinetic blood sample.

While in the CRU, the total daily nutritional composition should be approximately 50% carbohydrate, 35% fat and 15% protein. The daily caloric intake per subject should not exceed approximately 3200 kcal.

### **Alcohol and Caffeine**

Subjects will abstain from alcohol for 24 hours prior to admission to the CRU and continue abstaining from alcohol until collection of the final pharmacokinetic sample. Subjects may undergo an alcohol breath test at the discretion of the investigator.

Subjects will abstain from caffeine-containing products for 24 hours prior to the start of dosing until collection of the final pharmacokinetic sample.

### **Activity**

Subjects will abstain from unaccustomed strenuous exercise (e.g., heavy lifting, weight training, calisthenics, aerobics) for at least 48 hours prior to each blood collection for clinical laboratory tests. Regular routine exercise and walking at a normal pace will be permitted.

Subjects should have a normal day time awake, night time asleep cycle throughout the study.

### **Showering**

Subjects will briefly shower (approximately 5 minutes) once in the morning at least 30 minutes prior to the first application of study ointment using [REDACTED]

### **Clothing**

Subjects will be provided with cotton T-shirts and trousers to wear during the study.

## **4.6 Life Style Guidelines: Cohort 3**

Patients in Cohort 3 will be recommended to use old clothes or test the ointment on a small, unobtrusive area of clothing as this is a developmental formulation which has not been tested for compatibility with different types of fabric.

## **4.7 Contraceptive Requirements**

Contraceptive requirement for the study have been defined using the recent recommendations of the Clinical Trials Facilitation Group, Rome September 2014 meeting and also the EMA M3(R2) guidance.

### Females

Females of child-bearing potential must agree to use highly effective methods of contraception from screening to 60 days after the last study dose. Highly effective methods are:

- combined (estrogen and progestogen containing) hormonal contraception associated with inhibition of ovulation administered by oral or intravaginal route
- oral, injectable or implantable progestogen-only hormonal contraception associated with inhibition of ovulation
- intrauterine device (IUD)
- intrauterine hormone-releasing system ( IUS)
- bilateral tubal occlusion
- vasectomised partner
- true sexual abstinence, where this is in line with the usual lifestyle of the subject; periodic (calendar, ovulation, symptothermal or post-ovulation) abstinence and withdrawal are not acceptable methods of contraception.

Females are considered to be of non-child-bearing potential if they fulfill at least one of the following criteria:

- Postmenopausal, defined as 45 to 65 years of age and amenorrheic for at least 2 years PLUS have a serum follicle stimulating hormone (FSH) level within the laboratory's reference range for postmenopausal women, at screening.
- have undergone a documented hysterectomy and/or bilateral oophorectomy.

#### Males with partners who are WOCBP

Males with partners who are WOCBP must agree to use contraception from the start of dosing study ointment until 120 days after the last dose of study ointment.

#### **4.8 Subject Withdrawal and Replacement**

Subjects will be discontinued from the investigational product and potentially from the study in the following circumstances:

- 1 Enrollment in other clinical studies involving investigational products or enrollment in other types of clinical research judged not to be scientifically or medically compatible with this study.
- 2 The subject requests to be discontinued from the study.
- 3 Use of prohibited concomitant medications.
- 4 Sponsor decision to stop the study or to stop the subject's participation in the study for medical, safety, pharmacokinetic or regulatory, or other reasons consistent with applicable laws, regulations, and good clinical practices (GCP).
- 5 A severe or serious adverse event occurs that the investigator considers is related to study drug.

- 6 Any criteria for laboratory safety or vital sign values of Potential Clinical Concern (Appendix 1).
- 7 Any criteria for Hepatic Safety (Appendix 2).
- 8 Any criteria for ECG Values of Potential Clinical Concern (Appendix 3).

Subjects may have their study drug discontinued if they have abnormal laboratory results which are considered to be clinically significant as assessed by the investigator. This decision should be made in the best interest of the subject and follow up should be conducted using standard clinical practices. Subjects may also be temporarily discontinued from study drug while AEs and/or laboratory test abnormalities are being investigated and/or at the request of the sponsor's CMO. The investigator should discuss with Ziarco's CMO any subject for whom temporary or permanent discontinuation of study drug is being proposed. Subjects who discontinue early from the study should be asked to complete all the efficacy and safety assessments scheduled for the end of study assessment.

Subjects may withdraw from the study at any time without penalty and for any reason without prejudice to their future medical care. In all cases, the reason(s) for withdrawal, including the primary reason, must be recorded on the case report form (CRF). If a subject is prematurely withdrawn from the study for any reason, the investigator must make every effort to perform the evaluations described for the early termination/follow up visit (in clinic) and a further follow up contact (either by telephone or in clinic) 7 to 14 days later. Subjects who withdraw due to lack of efficacy (Cohort 3) or adverse events which may be attributed to double blind treatment will not be replaced.

Cohort 3 patients who withdraw due to personal reasons, poor compliance, other protocol deviations or are lost to follow up may be replaced until at least 30 evaluable patients have completed the study.

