### 7.3 Electrocardiogram (ECG) Recording

Single or triplicate (3 recordings over a 10 minute period) ECG recordings will be measured (see Section 6.7 schedule of activities for details). Measurements will be taken after the subject has rested for at least 10 minutes in a supine position using a 12-lead ECG machine.

To ensure safety of the subjects, a qualified individual at the investigator site will make comparisons to the baseline measurements. If the QTcF is  $\geq 60$  msec from baseline; or an absolute QTcF value is  $\geq 500$  msec for any ECG, the ECG intervals should be inspected carefully to ensure that the RR interval has been recorded correctly, and a single ECG will be repeated at 5-minute intervals up to 3 times to confirm any increased QT interval values. If the values are consistently high, the subject will be withdrawn from the study, allowed to return home (so long as no other clinical findings preclude this) and will be instructed to return for the follow up visit 7-14 days later.

In some cases, it may be appropriate to repeat abnormal ECGs to rule out improper lead placement as contributing to the ECG abnormality. It is important that leads are placed in the same positions each time in order to achieve precise ECG recordings. If a machine-read QTcF value is prolonged, as defined above, repeat measurements may

not be necessary if a qualified physician's interpretation determines that the QTcF values are acceptable for the individual.

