**Chemistry**

Total bilirubin	>1.5 times the upper limit of the reference range
AST	>3 times upper limit of the reference range
ALT	>3 times upper limit of the reference range
GGT	>3 times upper limit of the reference range
Alk Phosphatase	>3 times upper limit of the reference range
Creatinine	>1.3 times upper limit of the reference range
Urea	>1.3 times upper limit of the reference range
Glucose, fasting	<0.6 or >1.5 times the limits of the reference range
Uric acid	>1.2 times upper limit of the reference range
Sodium	<0.95 or >1.05 times the limits of the reference range
Potassium	<0.9 or >1.1 times the limits of the reference range
Calcium	<0.9 or >1.1 times the limits of the reference range
Albumin	<0.8 or >1.2 times the limits of the reference range
Total protein	<0.8 or >1.2 times the limits of the reference range

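### For Cohorts 2 and 3 the creatinine entry limit (1.5 x ULN) is looser than the mandatory stopping limit (1.3 x ULN), so a patient can be randomised while already meeting the stop

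*Protocol*

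**What the plan says.** **Stopping rule.** Protocol 4.8 opens: "Subjects will be discontinued from the investigational product and potentially from the study in the following circumstances". Item 6 in that list is "Any criteria for laboratory safety or vital sign values of Potential Clinical Concern (Appendix 1"). The creatinine entry in Appendix 1 (Chemistry) is ">1.3 times upper limit of the reference range".

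**Entry rule.** Protocol 4.4 criterion 13, for Cohorts 2 and 3, gives examples of excluding disease. One is "Renal insufficiency and/or serum creatinine" above 1.5 x ULN, with one retest allowed when the value is below 2 x ULN. Protocol 4.3 sets no numeric creatinine limit for Cohort 1.

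**Discretion elsewhere.** After the list, 4.8 adds: "Subjects may have their study drug discontinued if they have abnormal laboratory results which are considered to be clinically significant", as the investigator judges. It continues: "Subjects may also be temporarily discontinued from study drug while AEs and/or laboratory test abnormalities are being investigated". The investigator is also to discuss any proposed temporary or permanent discontinuation with the sponsor's Chief Medical Officer (CMO). Criterion 27 of 4.4 lets the investigator, in discussion with the CMO, exclude a patient whose laboratory abnormality raises the risk of participation or could confuse the results.

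**SAP.** SAP 10.4, Table 2, uses above 1.3 x ULN as the creatinine value of potential clinical concern.

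**The concern.** A stopping limit should sit at or beyond the entry limit, so that a patient who is fit to enter is not already due to stop. For creatinine the order is reversed. A patient at 1.4 x ULN passes criterion 13, is randomised, and on a plain reading of item 6 must come off drug without any change in renal function.

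What is at stake is consistent conduct and, at most, an occasional lost patient. Cohort 3 runs at up to four sites, and two of them could act differently on the same value. SAP 6.1 and 8 restrict post-baseline efficacy summaries to records up to one day after the last application, and the primary analysis in SAP 8.1 uses observed Week 2 values. A Cohort 3 patient stopped early for a baseline creatinine could therefore contribute no Week 2 value. A stop for a laboratory value is not among the reasons for replacement that 4.8 names for Cohort 3.

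**Working it through.** **1. The two limits side by side (Cohorts 2 and 3)**

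| Creatinine (x ULN) | 4.4 criterion 13 (>1.5 excludes) | 4.8 item 6 with Appendix 1 (>1.3 stops) |
|---|---|---|
| 1.3 | eligible | not met |
| 1.31 | eligible | met |
| 1.4 | eligible | met |
| 1.5 | eligible | met |
| 1.51 | excluded | met |

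The clash is confined to values above 1.3 and up to 1.5 x ULN.

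**2. Is the order deliberate?** The other parameters with numbers at both points suggest not.
- QTc: entry excludes above 450 msec; Appendix 3 starts at 500 msec.
- Pulse: entry excludes below 50 or above 100 bpm; Appendix 1 starts below 40 or above 120 bpm.
- ALT and AST: 4.3 excludes above 1.5 x ULN (4.4 gives that figure only in its retest clause); Appendix 1 starts above 3 x ULN.
- Total bilirubin: 1.5 x ULN at both points.

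Among these, only creatinine has its stop inside its entry limit. Appendix 1 also makes haemoglobin and haematocrit relative to baseline, but not creatinine.

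**3. When a scheduled result could trigger the clash** (Protocol 6.1, 6.3, 6.4 and Tables 10 and 11)
- Both cohorts: screening, and Day 1 before randomisation and dosing.
- Cohort 2 during dosing: Day 4, so one result. The last application is on the morning of Day 7 and the next sample is on Day 9.
- Cohort 3 between first and last dose: none. The last application is on the evening of Day 14 and the next sample is on Day 15.

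**4. Expected number of patients.** No frequency is given, so I assume that 0.5% to 2% of patients fall in the band. Expected number = n x proportion.
- Cohort 3, n = 30: 30 x 0.005 = 0.15; 30 x 0.02 = 0.6.
- Extra Cohort 3 screen failures if entry moves to 1.3 x ULN, about 45 screened: 45 x 0.005 = 0.23; 45 x 0.02 = 0.90.

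Cohort 2 is left out because Appendix 14 shows that its patients were already under treatment when the current Protocol version was written.

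**5. What one lost patient would cost.** Protocol 8.9 and SAP 3.3 state 80% power for 20 versus 10 patients, a difference of 30, an SD of 30 and a one-sided 5% test. The noncentrality is (30/30)/sqrt(1/n1 + 1/n2), with n1 + n2 - 2 degrees of freedom.
- 20 versus 10: 1/sqrt(0.05 + 0.1) = 2.582, 28 df, power 80.9%. This reproduces the stated figure.
- 19 versus 10 (one active patient lost): 2.560, 27 df, power 80.2%.
- 20 versus 9 (one placebo patient lost): 2.491, 27 df, power 78.3%.

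**The case against.** The best defence is that Appendix 1 is meant as a set of flags for clinical judgement. Protocol 3.7.1 cites it in connection with clinically significant abnormalities, and 4.8 itself follows the list with two permissive sentences on laboratory results. Every proposed discontinuation goes to one sponsor physician, which largely guards against sites diverging. Criterion 27, or the renal insufficiency wording in criterion 13, could keep such a patient out altogether. A literal reading errs towards stopping drug, so no safety protection is weakened.

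Most of this stands, and it is why the point is minor. It does not remove the conflict. The permissive sentences are not written as qualifiers of item 6 and can equally be read as an added discretionary stop for results outside Appendix 1. Neither the CMO discussion nor criterion 27 says which of the two limits governs.

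A reader might go further and infer a second contradiction, for QTcF, between item 8 ("Any criteria for ECG Values of Potential Clinical Concern (Appendix 3")) and Protocol 7.3. The documents do not support that. Section 7.3 uses the same QTcF limits as Appendix 3, 500 msec or a rise of 60 msec, and describes how a reading is verified: "a single ECG will be repeated at 5-minute intervals up to 3 times to confirm any increased QT interval values". It then withdraws the subject only if values stay high, and it allows a physician to accept the reading. That is the working procedure for the same limits, and what is missing is a cross-reference. Differing action between sites cannot arise for scheduled on-treatment ECGs either: Cohorts 1 and 2 run at a single centre, and Cohort 3 has no ECG scheduled during dosing.

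**Conclusion.** Wrong as written, and minor. For Cohorts 2 and 3, the entry and stopping limits for creatinine are in the wrong order, and the text does not settle which prevails above 1.3 and up to 1.5 x ULN.

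The reach is narrow. It covers the screening and Day 1 pre-dose samples in both cohorts, plus Day 4 in Cohort 2. In Cohort 3 it rests on a pre-dose value or an unscheduled repeat. The estimate of 0.15 to 0.6 Cohort 3 patients depends wholly on the assumed 0.5% to 2%, which nothing in the documents anchors; use of criterion 27 would lower it.

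It would be an over-reading to infer that the trial's statistical conclusions are at risk. No stated figure changes, and losing one patient moves power by at most 2.6 percentage points (80.9% to 78.3%) under the plan's own assumptions.

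**What to change.** In Protocol 4.4 criterion 13, lower the creatinine limit from 1.5 to 1.3 x ULN and keep the single retest for values below 2 x ULN. Entry and stopping then agree. Moving the entry limit is simpler than raising the Appendix 1 limit, because SAP Table 2 already uses 1.3 x ULN and needs no change.

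The cost is one short wording change, no new assessments, and slightly narrower eligibility: 0.2 to 0.9 extra screen failures among about 45 screened for Cohort 3, on the same assumption.

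As an optional editorial clarification, item 8 of 4.8 could refer to 7.3 for confirmation of QT/QTcF values.

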#### **4.9 Temporary Discontinuations**

A subject who misses one or more doses due to personal circumstances, or has an AE (not related to study drug), may be allowed to restart dosing after discussion between the investigator and CMO.

